Feasibility and Acceptability of a Beverage Intervention for Hispanic Adults

NCT02911753 (ClinicalTrials.gov)

Registered September 19, 2016. Last updated November 1, 2017

Aims and Study Hypotheses

This pilot study will expand on earlier research by our team using beverage interventions to enhance cardiometabolic health. This study's primary objective is to assess the feasibility and acceptability of a beverage intervention in obese Hispanic adults. Primary feasibility outcomes will be recruitment, retention, and acceptability. Beverage intake will also be assessed through intake diaries and beverage return rates during weekly clinic visits. The preliminary efficacy of the beverage intervention will assess changes in total cholesterol, high-density lipoprotein (HDL), and low-density lipoprotein (LDL) over 6-weeks. Secondary outcomes are changes in fasting glucose, hemoglobin A1c (HbA1c), and high-sensitivity C-reactive protein (hs-CRP). Our study will evaluate participant-reported tolerance and as an exploratory aim, our study will also assess safety/toxicity-related to renal and/or liver function as albeit limited, evidence from green tea polyphenol E supplementation studies have reported a few cases of hepatic toxicity with on-going supplementation [1]. Renal and hepatic toxicity function will be assessed at baseline and 6-weeks. The aforementioned outcomes will be examined to test the following hypotheses: a) recruitment and retention of obese Hispanic participants in a 6-week beverage intervention study is feasible; b) the consumption of green tea and Mediterranean lemonade will be well-tolerated with high adherence; and c) green tea and Mediterranean lemonade intake will result in an improved cardiometabolic profile at the end of 6-weeks.

Design and Methodology

Design

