At the completion of the study, participants will take part in an exit interview where they will be asked to rate their overall satisfaction with the intervention, if they would consider a longer-term beverage intervention, and finally, if they would recommend the program to others. Participants will also be asked questions regarding satisfaction with their overall progress and for changing dietary beverage habits. Each item will be rated on a Likert scale with higher scores indicating greater program favorability. Open-ended questions will be used to seek participant input on modifications that could be made to improve acceptability and effectiveness of the intervention.

The responses will be used to identify which recruitment and intervention components were well received, which could be improved, and which were not acceptable.

Efficacy Outcomes

Descriptive statistics, including means, ranges, and standard deviations, will be calculated for the primary efficacy outcomes, cholesterol/lipid levels, and the secondary outcomes: fasting glucose, HbA1c, and hs-CRP. Mixed models will be used to compare arms in each of these outcomes' change from baseline. We will include fixed effects of intervention arm, time and their interaction to allow for different patterns of change between the arms, as well as a random participant effect to account for the longitudinal nature of the data. Baseline values of the outcomes will be included in the dependent variable vector. The changes from baseline, and the differences between arms in change from baseline will be estimated using contrasts from the mixed models. Mixed models yield unbiased estimates for data that are missing completely at random (when missingness does not depend on any observed or unobserved data) and missing at random (when missingness may depend on observed data, such as the baseline value of the outcomes), as these models perform an implicit imputation [12, 13]. Data from all patients who are randomized will be analyzed in the arm that they were randomized to.

Sample Size Calculation

The total sample size of 50 will provide 95% confidence intervals for the primary feasibility outcomes (proportion of eligible participants who enroll and the proportion of participants retained in the study) that are no wider than 0.28 (\pm margin of error = 0.14), conservatively assuming a base proportion of 0.5, which maximizes the standard error. The trial will be

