considered feasible if the proportion retained is greater than 70%. If retention in the study is 81% or greater, the 95% confidence interval will not contain this 70% cutoff. Power will be insufficient to detect a minimum important difference of a 6 mg/dL change in fasting lipids from baseline, the primary efficacy outcome, based on variance estimates from a trial using a different fruit [14] (standard deviation ≈ 25 mg/dL). We acknowledge that we are not sufficiently powered to detect important differences between arms, but if the 95% confidence intervals for the comparison of the arms contain important differences we will take this as indication of a promising intervention. Variance components estimated from this study will be used to design an adequately powered trial.

Data Management

Data management will be conducted according to Good Clinical Practice guidelines to enhance data quality assurance and control. This will include standard operating procedures and staff trainings for data acquisition, entry, and processing. Further, information obtained from this research will be kept confidential to respect the participant's privacy. All records will be stored and locked in a file cabinet. In addition, all research databases will have password-controlled access, and the researchers will control this access. Data analyses will take place using a dedicated study computer upon study completion. No interim analyses will be performed. Study data will be uniquely coded for each subject and then entered via secure server to a Research Electronic Data Capture (REDCap) database maintained by the Clinical and Translational Sciences Research Center (CATS) at the University of Arizona. Only local study personnel will have access to identified study data. Once the study is complete the study records will be transferred to the University of Arizona storage facility and kept in accordance with applicable

laws. All participant data (including signed informed consent) will be stored for 6 years after the completion of the project. Results from this study will be disseminated through peer-reviewed manuscripts and presentations at national meetings. Participants will be provided with a lay summary of the research findings and the peer reviewed manuscripts.

List of Abbreviations:

Center of Disease Control (CDC)

Body mass index (BMI)

Epigallocatechin gallate (EGCG),

Sugar-sweetened beverages (SSBs)

hs-CRP (high-sensitivity C-reactive protein)

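### The rule for calling a drink promising rewards an effect that is merely not ruled out: at an SD of change of 25 mg/dL, an inert drink passes about 91% of the time

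*Combined protocol and SAP*

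**What the plan says.** All of this is in the combined protocol and SAP.

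- **Aims and Study Hypotheses.** The "primary objective is to assess the feasibility and acceptability of a beverage intervention in obese Hispanic adults". Efficacy on lipids is called preliminary. Even so, "The aforementioned outcomes will be examined to test the following hypotheses", and hypothesis (c) is that the two active drinks improve the cardiometabolic profile at 6 weeks.
- **Design.** Randomization is 2:2:1 to green tea, Mediterranean lemonade and flavored water, 50 participants in all.
- **Efficacy Outcomes.** For each outcome, "the differences between arms in change from baseline will be estimated using contrasts from the mixed models".
- **Sample Size Calculation.** "Power will be insufficient to detect a minimum important difference of a 6 mg/dL change in fasting lipids from baseline", "based on variance estimates from a trial using a different fruit", with an SD of about 25 mg/dL. Next comes "We acknowledge that we are not sufficiently powered to detect important differences between arms", and the same sentence goes on to the rule at issue: "if the 95% confidence intervals for the comparison of the arms contain important differences we will take this as indication of a promising intervention". The section ends its efficacy discussion with "Variance components estimated from this study will be used to design an adequately powered trial".

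Nothing elsewhere in the document qualifies the rule. It is the only instruction on how to interpret the between-arm efficacy intervals.

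**The concern.** The rule reads imprecision as encouragement. A wide interval contains almost everything, including important benefit, no effect and important harm. The plan looks only at whether an important difference lies inside, and if so attaches a favourable label. The drink need not look better than control, and the interval need not exclude zero or harm.

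Two things are at stake. First, the label would carry little information, because a drink with no effect would usually earn it. Second, the incentive runs the wrong way: for any true benefit smaller than 6 mg/dL, a smaller trial or more dropout makes the label easier to obtain. The plan commits to peer-reviewed papers and a lay summary for participants, so a prespecified favourable label could be repeated there as a finding.

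**Working it through.** **The section's own figures.** These reproduce.
- Half-width for a proportion of 0.5 with n = 50: 1.96 × √(0.25/50) = 0.139, width 0.277 (stated: 0.14 and 0.28).
- Wald lower limit at 81% retention: 0.81 − 1.96 × √(0.81 × 0.19/50) = 0.701, above 0.70 as stated.
- No power figure is given for efficacy. By a normal approximation, power to detect 6 mg/dL at SD 25 with 20 versus 10 is 9.0%, so the plan is right to call it insufficient.
- The plan states no pass rate for the rule.

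**Inputs.** Minimum important difference 6 mg/dL and SD about 25 mg/dL (Sample Size Calculation); N = 50 at 2:2:1, so 20:20:10 (Sample Size Calculation; Design); two-sided 95% intervals.

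**Readings the document does not settle.**
1. The 6 mg/dL, stated as a change from baseline, applies to between-arm differences. It is the only figure given.
2. Important means beneficial, as hypothesis (c) and the favourable label imply. A benefit is coded negative, as for total cholesterol and LDL.
3. The 25 mg/dL, not tied to a named lipid, is the SD of change.

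**Interval width, active drink versus flavored water, complete data.** SE = 25 × √(1/20 + 1/10) = 9.68. With 47 df, t = 2.012 and the half-width is 2.012 × 9.68 = 19.5 mg/dL. The lower limit reaches −6 unless the drink is observed about 19.5 − 6 = 13.5 mg/dL or more worse than control.

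**Pass rate.** For a true difference d, P(lower limit ≤ −6) is the noncentral-t distribution function at 2.012, with 47 df and noncentrality (d + 6)/SE.

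| True effect | d | Noncentrality | Pass rate |
|---|---|---|---|
| 12 mg/dL benefit | −12 | −0.62 | 99.5% |
| 6 mg/dL benefit | −6 | 0 | 97.5% |
| 3 mg/dL benefit | −3 | 0.31 | 95.1% |
| None | 0 | 0.62 | 91.2% |
| 6 mg/dL harm | +6 | 1.24 | 77.2% |

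A normal approximation gives 91.0% at no effect, Φ(1.96 − 0.62), and a simulation with pooled SD gives 91.2%. In the same simulation, with two inert drinks and one lipid, at least one drink passes in 96% of trials.

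**What a pass looks like when there is no effect.** In 82% of such trials the interval contains both a 6 mg/dL benefit and a 6 mg/dL harm; the rule counts only the first. About half of trials favour the drink by chance, and essentially all of these pass. So in about 91 − 50 = 41% of trials the drink earns the label while observed worse than control.

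**If 25 is an SD of levels.** Then SD of change = 25 × √(2(1 − r)), where r is the baseline to 6-week correlation. The document gives no r; these values are illustrations, not bounds.

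| r | SD of change | Pass, no effect | Pass, 6 mg/dL harm | Both ±6 inside, no effect |
|---|---|---|---|---|
| 0.3 | 29.6 | 93% | 82% | 85% |
| 0.5 | 25.0 | 91% | 77% | 82% |
| 0.8 | 15.8 | 84% | 52% | 68% |
| 0.9 | 11.2 | 73% | 23% | 45% |

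**Effect of precision (SD of change 25, 2:2:1).**

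| True effect | N = 50 | N = 250 | N = 1000 |
|---|---|---|---|
| None | 91% | 72% | 21% |
| 3 mg/dL benefit | 95% | 90% | 72% |
| 6 mg/dL benefit | 97.5% | 97.5% | 97.5% |

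With 70% retention and completers only (14:14:7, 32 df), the no-effect rate rises from 91% to 93%.

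**The case against.** The strongest reply is that this is a pilot. Feasibility and acceptability are primary, low power is admitted in the same sentence as the rule, and variance estimates go forward to a properly sized trial. No sample size, analysis or progression decision depends on the label. Read as a screen against discarding a useful drink too early, the rule misses a true 6 mg/dL benefit only 2.5% of the time. All of this limits the consequence, and asking whether an important effect is still possible is a fair pilot question. But the answer to that question is that the effect has not been ruled out, and calling it promising claims more.

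A second reply is that the 91% rests on three readings. It does. The document names no lipid for the 6 or the 25, and for HDL benefit runs the other way. If 25 is an SD of levels and the correlation is high, the rule separates harm from benefit much better: at r = 0.9, 23% against 97.5%. That stands, so the statement that the rule barely discriminates belongs to an SD of change of 25. An inert drink still passes 73% of the time at r = 0.9. If a difference in either direction counted as important, the rule would be met in effectively every trial at SD 25, because an interval with a half-width near 19.5 cannot fit between −6 and +6.

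A third reply is that another remedy exists, such as a condition on the point estimate. That is possible, but it would need its own justification at this sample size. Removing the label does not.

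**Conclusion.** Wrong as written. Containing an important difference is not a positive sign, and this holds whichever lipid, SD or direction is meant. On the three readings set out above, the rule labels an inert drink promising about 91% of the time, within 7 percentage points of a drink with the full 6 mg/dL benefit. Across the correlations illustrated for the other reading of the SD, the no-effect rate runs from 73% to 93%. The point should be fixed, but it is not grave: point estimates and intervals will be reported in any case, and the feasibility conclusions do not depend on it.

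**What to change.** In Sample Size Calculation, end the sentence on low power after its admission that the trial cannot detect important differences between arms. Replace the rest of that sentence with:

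> The between-arm 95% CIs for difference in change, each active drink vs flavored water, will be reported as the range of effects compatible with the data; a CI that merely contains an important difference will not be taken as evidence of benefit or promise.

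Keep the next sentence on variance components. Hypothesis (c) can stand, since the new wording does not bar a conclusion from an interval that excludes zero. The green tea versus lemonade contrast can still be reported.

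The cost is one clause of SAP text and the loss of the label. The estimates, intervals, mixed model, sample size and feasibility criteria are unchanged.
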